10.2.2 Adverse Event Overview

An overview of AEs will be presented consisting of the number and percentage of subjects experiencing at least one event for each of the following AE categories in each Safety Population:

- Any treatment-emergent AE

- Any treatment-emergent AE related to study drug according to the investigator
- Any severe treatment-emergent AE
- Any serious treatment-emergent AE
- Any treatment-emergent AE leading to discontinuation of study drug
- Any treatment-emergent AE leading to death
- Any treatment-emergent Areas of Safety Interest, as defined in [Appendix B](#).

All deaths will also be summarized:

- Deaths occurring \leq 140 days after last dose of RZB or \leq 28 days after last dose of APR
- Deaths occurring $>$ 140 days after last dose of RZB or $>$ 28 days after last dose of APR

10.2.3 Treatment-Emergent Adverse Events by SOC and/or PT

The number and percentage of subjects experiencing TEAEs will be tabulated using the Medical Dictionary for Regulatory Activities (MedDRA) system organ class and preferred term, by severity, and by relationship to the study drug as assessed by the investigator. When summarizing the number and percentages of subjects, subjects with multiple occurrences of the same adverse event will be counted once, and only the maximum severity level will be presented in the severity summaries, and the worst/highest relationship level in the relationship summaries.

In addition, treatment-emergent adverse events will be summarized by PT and sorted by decreasing frequency for the risankizumab group.

10.2.4 Treatment-Emergent Adverse Events per Patient-Years of Exposure

Exposure-adjusted AEs per 100 patient-years will be provided, where AEs per 100 patient-years of exposure are defined as the number of AEs divided by the total exposure in 100 patient-years.

Note that one event per preferred term per day per subject will be counted in the calculation of the number of TEAEs (i.e., a preferred term will not be counted twice on the same day for the same subject). The exposure-adjusted TEAE rate per 100 patient-years is calculated as:

$$100 \times \frac{\text{Number of TEAEs}}{\text{Total Patient Years}}$$

where total patient years in each period are defined below.

Total patient years in Period A:

Sum of study drug exposure in Period A, defined as

RZB arm: the minimum of (the last dose date in Period A + 140 days, the end of study date + 1 day, and the first dose date in Period B if not missing [and the cutoff date during the Primary Analysis for Period A + 1 day]) minus the first dose date in Period A, normalized by 365.25 and rounded to one decimal place.

APR arm: the minimum of (the last dose date in Period A + 28 days, the end of study date + 1 day, and the first dose date in Period B if not missing [and the cutoff date during the Primary Analysis for Period A + 1 day]) minus the first dose date in Period A, normalized by 365.25 and rounded to one decimal place.

Total patient years in Period B:

Sum of study drug exposure in Period B, defined as

RZB/RZB or APR/RZB arm: the minimum of (the last dose date in Period B + 140 days, and the end of study date + 1 day [and the cutoff date during the Primary Analysis for Period B + 1 day]) minus the first dose date in Period B, normalized by 365.25 and rounded to one decimal place.

APR/APR arm: the minimum of (the last dose date in Period B + 28 days, the first dose date of rescue RZB if not missing, and the end of study date + 1 day [and the cutoff date during the Primary Analysis for Period B + 1 day]) minus the first dose date in Period B, normalized by 365.25 and rounded to one decimal place.

Rescue RZB: the minimum of (the last dose date of rescue RZB + 140 days, and the end of study date + 1 day [and the cutoff date during the Primary Analysis for Period B + 1 day]) minus the first rescue RZB dose date, normalized by 365.25 and rounded to one decimal place.

Total patient years in the All-Risankizumab Treated Period:

Sum of study drug of risankizumab exposure, defined as the minimum of (the last risankizumab dose date + 140 days, and the end of study date + 1 day [and the cutoff date during the Primary Analysis for Period A + 1 day]) minus the first risankizumab dose date, normalized by 365.25 and rounded to one decimal place.

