- Period B (Week 16 to Week 52): Subjects initially randomized to risankizumab (Arm 1) will continue to receive risankizumab 150 mg as a single SC injection at Weeks 16, 28, and 40. Subjects initially randomized to apremilast (Arm 2) will be re-randomized at the Week 16 visit in a 1:1 ratio to receive either risankizumab 150 mg as a single SC injection at Weeks 16, 20, 32, and 44 (Arm 2a) or apremilast 30 mg orally BID up to Week 52 (Arm 2b). Rerandomization will be stratified by PASI 75 response (responder, non-responder) at Week 16. Rescue risankizumab will be offered to subjects who are re-randomized to apremilast (Arm 2b) and are PASI 50 non-responders at Week 28 (Arm 3a; rescue risankizumab will be administered at Weeks 28, 32, and 44) or Week 40 (Arm 3b; rescue risankizumab will be administered at Weeks 40 and 44). The final efficacy evaluation will take place at Week 52.

The schematic of the study is shown in [Figure 1](#). Further details regarding study procedures are located in the Operations Manual ([Appendix F](#)).

Figure 1. Study Schematic

RZB- Risankizumab  
 APR- Apremilast; \*dose titration Day 1 to Day 5  
 \*\*Stratified by PASI 75 Response Status (Yes/No)

↓ Rescue with RZB for APR arm will be offered to subjects < PASI 50 starting at Week 28 **OR** Week 40

BID = twice daily; PASI = Psoriasis Area Severity Index; SC = subcutaneous

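### SAP Section 10.2.4, read naturally, rounds each subject's exposure to 0.1 year before summing, which would shift Period B adverse-event rates by different amounts in different arms

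*SAP*

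**What the plan says.** SAP Section 10.2.4 introduces the rate with "The exposure-adjusted TEAE rate per 100 patient-years is calculated as" and gives 100 times the number of TEAEs over total patient-years. For Period B the denominator is introduced by "Sum of study drug exposure in Period B, defined as". For the two sequences that receive risankizumab (RZB/RZB and APR/RZB) the item summed begins "the minimum of (the last dose date in Period B + 140 days, and the end of study date + 1 day". For continued apremilast (APR/APR) it begins "the minimum of (the last dose date in Period B + 28 days, the first dose date of rescue RZB if not missing". Both can also be cut at the primary-analysis cutoff date plus 1 day. The first Period B dose date is then subtracted, and the result is "normalized by 365.25 and rounded to one decimal place".

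The same rounding clause closes all six definitions in the section: two for Period A, two for Period B, rescue risankizumab, and the pooled all-risankizumab period ("minus the first risankizumab dose date, normalized by 365.25 and rounded to one decimal place").

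Under SAP Section 10.1, safety summaries are presented by treatment group. Protocol Section 7.5 also asks for events per 100 patient-years for serious events, deaths and events leading to discontinuation. Neither document plans a rate ratio, a test or a margin for these rates.

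**The concern.** First dose, last dose, rescue and end-of-study dates belong to a subject; an arm has no last dose date. The division by 365.25 and the rounding therefore attach most naturally to each subject's exposure, before the sum. SAP Section 6.0 supports this. It uses the same date construction for treatment duration, which it summarises by mean, standard deviation and median, so there it is plainly a subject-level quantity, and it carries no rounding.

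A tenth of a year is 36.5 days, which is coarse for exposures of roughly 250 to 340 days. Because dosing is on a fixed schedule, unrescued completers in one arm have nearly the same exposure, so their rounding errors tend to share a sign and do not average out as they would if exposures were widely spread.

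Period B compares arms with unequal follow-up windows (140 against 28 days) and with apremilast exposure cut at rescue. Events per 100 patient-years is the planned summary that takes account of exposure, and an arm-dependent error in the denominator passes straight into it.

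**Working it through.** The SAP states no exposure total or rate, so there is no figure of its own to reproduce.

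**Inputs**
- Visit days, from the Study Activities Table in Protocol Appendix D: Week 16 = Day 113, Week 28 = 197, Week 40 = 281, Week 44 = 309, Week 52 = 365; visit window ±3 days.
- RZB/RZB doses, Protocol Section 4.1: "risankizumab 150 mg as a single SC injection at Weeks 16, 28, and 40".
- Re-randomised arms, same section: "Weeks 16, 20, 32, and 44 (Arm 2a) or apremilast 30 mg orally BID up to Week 52 (Arm 2b".
- Tails of 140 and 28 days, and the cut at rescue: SAP Section 10.2.4.

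**Formulas**
- Exposure = end date by the SAP minimum rule − first Period B dose.
- Rate factor = (days / 365.25) / (the same, rounded to 0.1). A factor above 1 means that the reported rate is too high.
- Cross-arm distortion = rate factor of the risankizumab arm / rate factor of APR/APR.

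**On schedule, full tail, per-subject rounding**

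| Path | Days | Years | Rounded | Effect on rate |
|---|---|---|---|---|
| RZB/RZB | 281 + 140 − 113 = 308 | 0.8433 | 0.8 | +5.4% |
| APR/RZB | 309 + 140 − 113 = 336 | 0.9199 | 0.9 | +2.2% |
| APR/APR, never rescued | 365 + 28 − 113 = 280 | 0.7666 | 0.8 | −4.2% |
| APR/APR, rescued Week 28 | 197 − 113 = 84 | 0.2300 | 0.2 | +15.0% |
| APR/APR, rescued Week 40 | 281 − 113 = 168 | 0.4600 | 0.5 | −8.0% |

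With no rescue, RZB/RZB against APR/APR is 1.0541 / 0.9582 = 1.100, and APR/RZB against APR/APR is 1.0221 / 0.9582 = 1.067.

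**Rescue (shares assumed; the documents give none)**

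Worked example, 40% at Week 28 and 10% at Week 40:
- Mean exact exposure is 0.5 × 280 + 0.4 × 84 + 0.1 × 168 = 190.4 days = 0.5213 years.
- Mean rounded exposure is 0.5 × 0.8 + 0.4 × 0.2 + 0.1 × 0.5 = 0.53 years.
- The APR/APR factor is 0.5213 / 0.53 = 0.9836.

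| Rescued Week 28 / Week 40 | RZB/RZB vs APR/APR | APR/RZB vs APR/APR |
|---|---|---|
| 0% / 0% | +10.0% | +6.7% |
| 0% / 30% | +10.9% | +7.6% |
| 20% / 10% | +9.0% | +5.7% |
| 40% / 10% | +7.2% | +3.9% |
| 60% / 10% | +4.4% | +1.2% |
| 80% / 0% | 0.0% | −3.0% |

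With rescue at Week 28 only, the APR/APR error itself is zero at about 53% rescued. The distortion changes sign beyond about 67% (APR/RZB) and 80% (RZB/RZB).

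**Visit timing.** The RZB/RZB exposure of 308 days lies 2.5 days below the 0.85-year threshold (310.5 days). If first and last dose days vary independently and uniformly over ±3 days (assumption), 10 of 49 combinations round up to 0.9. The RZB/RZB distortion falls from 10.0% to 7.3%; APR/RZB stays at 6.7%.

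**Early end of study.** Exposure ending the day after Week 52 is 366 − 113 = 253 days = 0.6927, rounded to 0.7, for every unrescued subject in every arm. The distortion is then nil. If half of the subjects in each arm end there, it is 5.3% and 3.6%.

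**Period A.** On schedule both arms have 113 − 1 = 112 days = 0.3066, rounded to 0.3. Both rates rise by 2.2%, so the comparison is not affected.

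**All-risankizumab period.** A continuous-risankizumab completer has 281 + 140 − 1 = 420 days = 1.1499, rounded to 1.1; at 421 days (1.1526) it rounds to 1.2. One day moves the counted exposure by 0.1 year. There is no comparator here.

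**If only the arm total is rounded.** The error is at most 0.05 patient-years: 0.05% of 92.8 (110 RZB/RZB subjects), 0.09% of 55.2 (60 APR/RZB) and 0.11% of 46.0 (60 APR/APR). Group sizes are from SAP Section 2.4.

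**The case against.** The strongest reply is that the quantity being defined is a total, so the rounding may describe only how that total is reported; nothing beside the rounding says that it applies to each subject. This stands as a possible reading, and under it the matter is negligible. It is the less natural reading, because the clause closes an expression that only makes sense for one subject.

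The size also depends on conditions. Errors within APR/APR differ in sign between subjects rescued at Week 28, rescued at Week 40 and never rescued, and ordinary visit timing pushes some RZB/RZB subjects over a rounding threshold. Protocol Section 5.6 waives the follow-up call for subjects who start commercial drug, so some may end at Week 52. The cutoff at the Period B primary analysis may shorten tails further, although the final analysis after study completion need not be cut there. All of this stands and limits what can be said about magnitude.

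Lastly, adverse-event percentages by arm do not use this denominator, and no efficacy result or type I error is involved. That stands too, and it keeps the point one of safety reporting.

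**Conclusion.** The point holds as an unclear rule that, followed in its natural sense, puts an arm-dependent error into the Period B exposure-adjusted rates. For on-schedule, never-rescued completers with full follow-up, the group rates shift by +5.4%, +2.2% and −4.2%. Setting the risankizumab rates beside the apremilast rate would overstate them relatively by about 10% (RZB/RZB) and 7% (APR/RZB). These figures describe that subject type and do not forecast the trial. The assumed settings with substantial Week 28 rescue give smaller values, and very heavy Week 28 rescue reverses the sign.

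A reader might infer that the plan certainly rounds each subject, that the arms are always distorted in opposite directions, and that a risankizumab-to-apremilast rate ratio will be inflated by 7–10%. The documents do not support this. The wording leaves a second reading open. At assumed rescue of 60%/10% the APR/APR rate is itself slightly too high (factor 1.0097), so the directions no longer oppose. The rescue share, cutoff timing and share ending at Week 52 are not given. The SAP reports rates by group, and the ratio is used here only to measure the error.

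**What to change.** In all six definitions in SAP Section 10.2.4, remove the rounding from the exposure expression. State once that days of exposure are summed unrounded over subjects in the arm, that the sum is divided by 365.25, that the rate is computed from this unrounded total, and that only the displayed arm total is rounded to one decimal.

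This settles both readings, removes the error whatever the rescue share or visit timing, and costs only SAP wording. It needs no new data and no change to the design.

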Each ITT Population will have a corresponding Safety Population, consists of subjects who received at least one dose of study drug during the specific Study Period. In addition, an all risankizumab treated (ALL_RZB) Population will be utilized for a comprehensive safety summary of RZB. The ALL_RZB Population is defined as all subjects who receive at least one dose of RZB as the study drug.

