6.0 Study Drug Duration and Compliance

Duration of treatment will be summarized by treatment groups among the Safety_A, Safety_B_R, Safety_B_NR, and Safety_Res Populations as well as the RZB group in the Safety_LT Population. In addition, duration of any RZB will be summarized among the ALL_RZB Population.

The duration of RZB for each period is defined as follows:

Period A: the minimum of (the last dose date in Period A + 84 days, the end of study date + 1 day, and the first dose date in Period B if not missing [and cutoff date during the Primary Analysis for Period A + 1 day]) minus the first dose date in Period A.

Period B: the minimum of (the last dose date in Period B + 84 days, and the end of study date + 1 day [and cutoff date during the Primary Analysis for Period B + 1 day]) minus the first dose date in Period B.

Rescue RZB: the minimum of (the last dose date of rescue risankizumab + 84 days, the end of study date + 1 day [and cutoff date during the Primary Analysis for Period B + 1 day]) minus the first dose date of rescue risankizumab.

ALL_RZB: the minimum of (the last dose date of risankizumab + 84 days, and the end of study date + 1 day [and cutoff date during the Primary Analysis for Period B + 1 day]) minus the first dose date of risankizumab.

The duration of APR for each period is defined as follows:

Period A: the minimum of (the last dose date in Period A + 1 day, the end of study date + 1 day, and the first dose date in Period B if not missing [and cutoff date during the Primary Analysis for Period A + 1 day]) minus the first dose date in Period A.

Period B: the minimum of (the last dose date in Period B + 1 day, the start date of rescue RZB if applicable, and the end of study date + 1 day [and cutoff date during the Primary Analysis for Period B + 1 day]) minus the first dose date in Period B.

Duration of treatment will be summarized by descriptive statistics of mean, standard deviation, median, minimum and maximum, among the number of subjects treated in each period.

Treatment compliance will be summarized by treatment groups among the Safety_A, Safety_B_R, Safety_B_NR, and Safety_Res Populations as well as the RZB group in the Safety_LT Population.

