9.0 Efficacy Analyses

9.1 General Considerations

All efficacy analyses will be conducted among the ITT Population in each analysis period. All tests will be 2-sided at an alpha level of 0.05.

The Primary Analysis for Period A will be performed after all ongoing subjects have completed Week 16 and all data pertaining to Period A are cleaned. This will be the only and final analysis for efficacy in Period A.

The Primary Analysis for Period B will be performed after all ongoing subjects have completed Week 52 and all data pertaining to Period B are cleaned. This will be the only and final analysis for efficacy in Period B.

The final analysis will be performed upon study completion.

Categorical Endpoints:

For categorical endpoints, the number and proportion of subjects who achieved the endpoint, as well as the 95% confidence interval (CI) of that proportion, will be provided by each treatment group among all ITT Populations.

In addition, comparisons between treatment groups will be made in the following analyses, with the estimated treatment difference, as well as the corresponding 95% CI and the p-value provided among the following populations:

- ITT_A Population: Comparisons in Period A will be made between RZB and APR using the Cochran-Mantel-Haenszel (CMH) test, adjusting for the actual values of stratification factors at Baseline: Baseline body weight (≤ 100 kg, > 100 kg) and prior exposure to any systemic and/or biologic treatment for psoriasis ($0, \geq 1$). In case of any stratum with zero subject in either treatment group, no stratification factor will be controlled.
- ITT_B_NR Population: Comparisons in Period B will be made between APR/RZB and APR/APR using the chi-square test.

- ITT_B_Combined Population: Comparisons in Period B will be made between APR/RZB and APR/APR using the CMH test, adjusting for the actual values of the stratification factor of re-randomization: PASI 75 response status at Week 16 (Yes/No). In case of any stratum with zero subject in either treatment group, no stratification factor will be controlled.

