10.0 Safety Analyses

10.1 General Considerations

Safety data will be summarized among the Safety_A, Safety_B_R, Safety_B_NR, and Safety_LT Populations. Safety summaries will be presented by treatment group. For the safety analysis, subjects are analyzed based on the treatment actually received, determined by the first dose of study drug that the subject received during the specific analysis period.

The overview of TEAEs, and potentially clinically important (PCI) findings in laboratory variables and vital sign variables will also be summarized among the Safety_B_Combined, Safety_Res, and ALL_RZB Populations.

Missing safety data will not be imputed.

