10.2.1 Treatment-Emergent Adverse Events

A treatment-emergent adverse event (TEAE) in each analysis period is defined as follows:

A TEAE in Period A is defined as any AE with an onset date on or after the first dose of study drug in Period A, and

- Within the minimum of (i) 140 days after the last dose of RZB in Period A and (ii) the first dose date of study drug in Period B for subjects who receive RZB at Baseline.
- Within the minimum of (i) 28 days after the last dose of APR in Period A and (ii) the first dose date of study drug in Period B for subjects who receive APR at Baseline.

A TEAE in Period B is defined as any AE with an onset date on or after the first dose of study drug in Period B and

- Within 140 days after the last dose of RZB in Period B for subjects who receive RZB in Period B.
- Within the minimum of (i) 28 days after the last dose of APR in Period B and (ii) the first dose date of rescue risankizumab (if any) for subjects who receive APR in Period B.

A TEAE during the administration of rescue risankizumab is defined as any AE with an onset date on or after the first dose of rescue risankizumab and within 140 days after the last dose of rescue risankizumab.

A TEAE during the administration of risankizumab (i.e., among the ALL_RZB Population) is defined as any AE with an onset date on or after the first dose of risankizumab and within 140 days after the last dose of risankizumab.

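### The ALL_RZB patient-years formula names only the Period A analysis cutoff, so it has no data cutoff at the Period B primary analysis

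*SAP*

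**What the plan says.** SAP Section 4.0 sets the population: "The ALL_RZB Population is defined as all subjects who receive at least one dose of RZB as the study drug". It therefore includes subjects randomized to risankizumab, subjects switched at Week 16 and subjects rescued at Week 28 or 40.

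Two exposure quantities are defined for it, each as the minimum of several dates minus the first risankizumab dose date:

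- **Patient-years (SAP Section 10.2.4).** Last dose + 140 days, end of study + 1 day, and a bracketed cutoff: "and the cutoff date during the Primary Analysis for Period A + 1 day]) minus the first risankizumab dose date".
- **Duration (SAP Section 6.0).** Last dose + 84 days, end of study + 1 day, and a different bracketed cutoff: "and cutoff date during the Primary Analysis for Period B + 1 day]) minus the first dose date of risankizumab".

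In the same Section 10.2.4, the RZB/RZB, APR/RZB and APR/APR rows for Period B name the Period B cutoff. So does the rescue row: "and the cutoff date during the Primary Analysis for Period B + 1 day]) minus the first rescue RZB dose date". The Period A rows name the Period A cutoff.

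The matching adverse-event window in Section 10.2.1 is "any AE with an onset date on or after the first dose of risankizumab and within 140 days after the last dose of risankizumab". Section 9.1 places the two primary analyses after ongoing subjects finish Week 16 and Week 52 respectively, and adds: "The final analysis will be performed upon study completion".

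**The concern.** Each single-period formula carries the cutoff of its own period, so the bracket reads as a term that is active at the analysis it names. That works for a population confined to one period. ALL_RZB is not confined to one, and its two formulas name different cutoffs without explanation.

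At the Period B primary analysis the patient-years formula then has no active cutoff. A subject who has passed Week 52 but is awaiting the safety call, with no end-of-study date, is credited with time up to last dose + 140 days. Events in that time have not been observed and cannot enter the numerator. The denominator is too large and the event rate too low.

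Section 6.0 would have the mirror gap at the Period A analysis, but only if ALL_RZB duration is reported then. The SAP does not say whether it is.

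**Working it through.** **Timeline check.** Protocol Section 4.1 gives a study duration of about 69 weeks for risankizumab and 61 for apremilast. Screening 5 + last dose Week 44 + 20 = 69. Screening 5 + 52 + 4 = 61. Both reproduce, so the schedule can be used.

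**Per-subject excess at the Period B analysis.** Take a subject at Day 365 on the cutoff date, with no end-of-study date. No cutoff: last dose day + 140 − first dose day. With a Period B cutoff: 365 + 1 − first dose day.

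| Group | First / last dose day | No cutoff (days) | With cutoff (days) | Excess (days) |
|---|---|---|---|---|
| Arm 1 | 1 / 281 | 420 | 365 | 55 |
| Arm 2a | 113 / 309 | 336 | 253 | 83 |
| Arm 3a | 197 / 309 | 252 | 169 | 83 |
| Arm 3b | 281 / 309 | 168 | 85 | 83 |

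**Population excess.** The documents give no accrual length or rescue rate. Assumptions:
- 110 subjects in each of Arm 1, APR/RZB and APR/APR (planned 110 and 220, the latter split 1:1).
- Full dosing and no dropout.
- 20% of APR/APR rescued (22 subjects, half at each rescue visit).
- Uniform entry over A days.
- Cutoff at the last subject's Week 52.
- End-of-study date missing for everyone still in follow-up.

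A subject who entered v days before the last one has excess max(0, e − v), with e = 55 or 83. The mean is e²/(2A), where 55²/2 = 1512.5 and 83²/2 = 3444.5.

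No-cutoff total: (110×420 + 110×336 + 11×252 + 11×168) / 365.25 = 87,780 / 365.25 = 240.3 patient-years.

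Excess at 52 weeks (A = 364): (110×1512.5 + 132×3444.5) / 364 = 1706.2 days = 4.67 patient-years.

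| Accrual (weeks) | No cutoff | With Period B cutoff | Overstated |
|---|---|---|---|
| 26 | 240.3 | 231.0 | 4.0% |
| 52 | 240.3 | 235.7 | 2.0% |
| 78 | 240.3 | 237.2 | 1.3% |
| 104 | 240.3 | 238.0 | 1.0% |

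Varying rescue from 0 to 35% gives 3.7–4.3%, 1.8–2.1%, 1.2–1.4% and 0.9–1.0%. If only 85% of apremilast subjects are re-randomized (20% rescued), the figures are 3.9%, 1.9%, 1.3% and 0.9%. In the 26-week row the rate is multiplied by 231.0/240.3 = 0.961, so it is 3.9% too low.

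**Later cutoff (20% rescued).** A lag of 28 days reduces e to 27 and 55, and the excess to 0.4–1.5% across the four accrual lengths. At 56 days it is at most 0.3%. At 84 days it is zero, because 83 < 84.

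**Mirror gap, only if ALL_RZB duration is reported at the Period A analysis.** With the 84-day tail and 20% rescued, no cutoff against a Period A cutoff gives 118.6 vs 90.0, 159.8 vs 140.0, 174.3 vs 161.0 and 181.5 vs 171.6 patient-years at 26, 52, 78 and 104 weeks. That is about 6 to 32% too high.

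**The case against.** **The excess may be close to nothing.** The SAP does not state the cutoff date, and the analysis follows completion of Week 52 and data cleaning. A cutoff 84 days after the last Week 52 visit removes the excess. Protocol Sections 5.6 and 6.1 also waive the follow-up call for subjects who start commercial drug. If their end-of-study date is Week 52, the formula's own end-of-study term already caps them. With half the subjects in that position and 20% rescued, the excess is 0.5–2.2%. These points stand, and they are why the range starts at zero. They do not give the formula a cutoff.

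**The reach is limited.** Section 10.1 says that the TEAE overview and the laboratory and vital-sign findings "will also be summarized among the Safety_B_Combined, Safety_Res, and ALL_RZB Populations". That overview counts subjects: "An overview of AEs will be presented consisting of the number and percentage of subjects experiencing at least one event". Neither output uses patient-years. This also stands, but Section 10.2.4 still defines an ALL_RZB denominator, and it should be computable as written.

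**A stronger reading is tempting.** A reader might take the Period A cutoff as always part of the minimum. At the Period B analysis the formula would then drop exposure after the Period A cutoff, while the adverse-event window ran on. With 52 weeks' accrual and 20% rescued, it would give 145.6 patient-years instead of 235.7, a 1.62-fold inflation of the rate. The documents do not support this as the intended rule. The bracket is set apart in the same way in every formula, it refers to the cutoff during a named analysis, and the literal version gives negative time for a rescue subject first dosed after that cutoff (113 + 1 − 197 = −83 days for a subject at Week 16 on the cutoff day, later rescued at Week 28). It is a programming risk, not the natural meaning.

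**Nor do the per-subject excesses carry over to the population.** If all 110 Arm 1 and 110 Arm 2a subjects were at Week 52 on the cutoff date, the excess would be 41.6 on 186.1 patient-years (22%), ignoring rescue. That requires everyone to have entered at once.

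**Conclusion.** The point holds as a minor defect in a definition. The rule as written does not give a properly cut ALL_RZB denominator at the Period B primary analysis. No figure stated in the plan is wrong.

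On the natural reading, patient-years are overstated by roughly 0 to 4% and the rate is slightly too low. The upper end needs short accrual, a cutoff exactly at the last subject's Week 52, and missing end-of-study dates throughout follow-up. The Section 6.0 gap is conditional on ALL_RZB duration being tabulated at the Period A analysis.

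The effect is descriptive and limited to the two primary-analysis snapshots. At the final analysis both formulas work if the brackets lapse. Efficacy results, type I error control and power are not touched.

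**What to change.** In the ALL_RZB formulas of SAP Sections 10.2.4 and 6.0, replace the named cutoff with *the cutoff date of the analysis being run + 1 day*, and state that no cutoff applies at the final analysis. Count ALL_RZB treatment-emergent events to the same date.

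Alternatively, state that ALL_RZB is not analysed at the Period A primary analysis and use the Period B cutoff in both formulas. Without that statement, changing A to B in Section 10.2.4 would only move the gap. If ALL_RZB rates were produced at the Period A analysis, patient-years would be 195.8 instead of 147.1 (33% too high) with 52 weeks' accrual and 20% rescued.

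Either option costs SAP wording only.
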